## 7.0 DRUG THERAPY

Not applicable to this study.

## 8.0 SURGERY

Not applicable to this study.

## 9.0 OTHER THERAPY

Not applicable to this study.

## **10.0 TISSUE/SPECIMEN SUBMISSION**

Not applicable to this study.

## **11.0 PATIENT ASSESSMENTS**

11.1 Study Parameters: See Appendix I.

### 11.2 Neurocognitive Evaluation

#### 11.2.1 Summary of Required Neurocognitive Tests for All Patients

The tests will be used to assess neurocognitive function. These tests are to be administered by a certified examiner (a health care professional such as a physician, nurse or data manager certified to administer the tests) Certification from other RTOG/ECOG studies is acceptable,

#### 11.2.2.1 Hopkins Verbal Learning Test (HVLTR)

The HVLTR incorporates 6 different forms, helping to mitigate practice effects of repeated administrations. Each form includes 12 nouns (targets) with 4 words drawn from 3 semantic categories, which differ across the 6 forms. The version used in RTOG 0933 involves memorizing a list of 12 targets for 3 consecutive trials (immediate recall), identifying the 12 targets from a list of semantically related or unrelated items (immediate recognition), and recalling the 12 targets after a 20-minute delay (delayed recall). Raw scores are derived for total recall, delayed recall, retention (percentage retained), and a recognition discrimination index. Each patient will serve as his/her own control, as the difference in scores obtained at baseline and at pre-specified post-treatment intervals will be calculated.

#### 11.2.2.2 Trail Making Test (TMT)

This is a measure of visuospatial scanning, attention, sequencing, and speed Part A and executive function in Part B. Patients must “connect the dots” either in a numbered sequence or alternating letters and numbers. Generally Part A and Part B require less than 5 minutes, and Part A is discontinued at 3 minutes, Part B at 5 minutes, to reduce burden on patients with significant cognitive impairment.

#### 11.2.2.3 Controlled Word Association Test (COWAT)

The patient produces as many words as possible in 1 min. (each) for a specific letter (C, F, L or P, R, W). Requires about 5 min to complete. Assesses language and executive/frontal skills.

#### 11.2.2.4 Mini-Mental Status Examination (MMSE)

This is a brief, standardized tool to grade patients’ global cognitive function. The MMSE begins with an assessment of orientation to place and time. Next is a test of memory (immediate recall) by having the subject immediately repeat the names of 3 objects presented orally. Following this the patient subtracts sevens serially from 100. The subject is then asked to recall the three items previously repeated (delayed recall). The final section evaluates aphasia and apraxia by testing naming, repetition, compliance with a 3-step command, comprehension of written words, writing, and copying a drawing. The maximum score that can be obtained for the entire MMSE is 30 points. There is no specific training to perform MMSE as the questions and conduct are straightforward and this is not a validated metric like the others.

### 11.3 Fatigue Evaluation

Fatigue will be assessed using the Multidimensional Fatigue Inventory (MFI-20).

#### 11.3.1 Summary of Required Fatigue Evaluations For All Patients

##### 11.3.1.1 Multidimensional Fatigue Inventory (MFI-20)

The MFI-20 is a multidimensional, self-report instrument designed to measure fatigue. It covers the following dimensions: General Fatigue, Physical Fatigue, Mental Fatigue, Reduced Motivation and Reduced Activity. A subscore from 4 to 20 is reported for each dimension, with 20 corresponding to maximal fatigue.

#### 11.4 Quality of Life Assessments

##### 11.4.1 Summary of Quality of Life Assessments

###### 11.4.1.1 FACT-BR (Appendix VI)

The FACT-BR is a multidimensional, self-report QOL instrument specifically designed and validated for use with brain malignancy patients. It is written at the 4th grade reading level and can be completed in 5-10 minutes with little or no assistance in patients who are not neurologically incapacitated. It measures quality of life related to symptoms or problems across 5 scales: physical well-being (7 items); social/family well-being (7 items); emotional well-being (6 items); functional well-being (7 items); and concerns relevant to patients with brain tumors (23 items). Items are rated on a five-point scale: 0-“not at all”, 1-“a little bit”, 2-“somewhat”, 3- “quite a bit” and 4-“very much”. FACT-BR is self-administered and does not require precertification. It has been translated into 26 languages and is available free of charge to institutions with the completion of an agreement. Form is available in English and Spanish.

###### 11.4.1.2 EQ-5D (Appendix VII)

The EQ-5D health related quality of life questionnaire will be used as well. EQ-5D is a standardized instrument for use as a measure of health outcome. Applicable to a wide range of health conditions and treatments, it provides a simple descriptive profile and a single index value for health status. . The US version of the EQ-5D will be used, to enable mapping of general HR-QoL scores from EQ-5D scores into health state utility scores (ranging from 0 to 1) for the US population. These utility scores are needed for cost-utility analysis (estimates of costs per “quality adjusted” life-year gained). Form is available in English and Spanish. This form can be completed in less than 5 minutes and is a two page questionnaire.

#### 11.5 Administration of Neurocognitive, Fatigue, and Quality of Life Assessments

##### 11.5.1 Timing

11.5.1.1 Prior to initiation of treatment, all patients will undergo baseline neurocognitive, fatigue, and quality of life testing using this test battery. At that time, history regarding level of education reached will also be obtained. After completion of radiotherapy, all patients will undergo neurocognitive and fatigue evaluation at 3, 6, 9, 12, and 24 months after WBRT-HA/SIB.

11.5.1.2 Examiners will give patients a short break if the patient appears fatigued or otherwise in need of a few-minutes break.

#### 11.6 Measurement of Response

Patients will undergo brain MRI prior to study entry (the MRI obtained for hippocampal contouring can be used for this purpose) and every 3 months until death or until 2 years after WBRT-HA/SIB, whichever comes first.

##### 11.6.1 Criteria for CNS Progression

###### 11.6.1.1 Assessment

The the bidimensional product for each of the 1-3 largest brain metastases identified at baseline will be recorded. The bidimensional product is defined as the largest dimension multiplied by the second largest dimension that is perpendicular to it (the largest dimension). This value will be recorded on the baseline form and every subsequent follow-up form. The appearance (yes/no and number) of any new brain metastases within the whole brain minus the hippocampal region will be recorded on all follow-up forms. The appearance (yes/no and number) of any new brain metastases within the hippocampal avoidance region (the hippocampus plus 5 mm) will be recorded on all follow-up forms.

Recurrences will be categorized as either within the hippocampal avoidance region or elsewhere within the brain. Therefore, there will be 3 kinds of local recurrences

reported: a) in the brain, b) in the hippocampal avoidance region, and c) elsewhere in the brain.

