#### 1.4 Feasibility of Hippocampal Avoidance and Integrated Boost During WBRT

In general, hippocampal avoidance poses important challenges in conformally avoiding the centrally located hippocampus with its unique anatomic shape, while allowing for uniform dose delivery to the remainder of the brain. In a recent dosimetric analyses of 30 Gy in 10 fractions prescribed to the whole brain, intensity-modulated radiotherapy (IMRT) allowed for the delivery of highly conformal dose distributions, maintaining the hippocampal volume receiving 10 Gy or higher (V10) to less than 50% and the maximum dose to the hippocampus to less than 16 Gy (Gondi 2010a). Coupling hippocampal avoidance with a more heterogeneous plan than delivers a higher volume to radiographically evident disease has also been demonstrated in a single treatment plan (Gutierrez 2007). Multiple institutions have also demonstrated the feasibility of WBRT with hippocampal avoidance utilizing LINAC-based IMRT delivery systems broadly available at multiple academic and community radiation oncology practices (Gondi 2010a). Incorporating an integrated boost into a WBRT with hippocampal avoidance has been demonstrated as well (Hsu 2010).

Avoiding the hippocampus poses the risk of attenuating the benefit of WBRT due to increased metastatic disease within the hippocampal conformal avoidance region. The magnitude of this risk has been reported in a study reviewing the MR images of 100 patients, 98 of whom received WBRT with or without SRS boost (Ghia 2007). T1-weighted, three-dimensional spoiled gradient, post-contrast axial MRI images with a 1.25 mm slice thickness, obtained prior to radiotherapy, were reviewed. In the 100 patients, 272 metastases were identified and analyzed. Out of the 272 metastases, 3.3% were within 5 mm of the hippocampi (n=9); 4.4% of metastases were between 5 to 10 mm from the hippocampi (n=11); and 6.3% of metastases lay between 10 and 15 mm from the hippocampi (n=17). Of all metastases, 86.4% were greater than 15 mm from the hippocampi (n=235). However, none of the metastases lay within the hippocampi. The upper 95% confidence limit for the risk of finding a metastatic lesion within 5 mm of the hippocampi at the time of presentation was 15.2%. An update of this study reported on an additional 271 patients with up to 10 brain metastases (Gondi 2010b). Of these

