### **2.2 Secondary Objectives**

- 2.2.1 Evaluate time to neurocognitive failure as measured by cognitive decline on a battery of tests: the HVLT-R for free recall, delayed recall, and delayed recognition; the Controlled Word Association Test (COWAT); the Trail Making Test Parts A and B (TMT); the Medical Outcomes Scale-Cognitive Functioning Subscale (MOS); and the Mini-Mental Status Examination (MMSE) after WBRT-HA/SIB for brain metastases
- 2.2.2 Evaluate fatigue, as assessed by the Multidimensional Fatigue Inventory (MFI-20) after WBRT-HA/SIB for brain metastases.
- 2.2.3 Evaluate local control within the brain
  - 2.2.3.1 Evaluate local control of brain metastases treated with integrated boost
  - 2.2.3.2 Evaluate local control within the region of brain within the CTV receiving 20 Gy.
  - 2.2.3.3 Evaluate local control within the hippocampal regions.
- 2.2.4 Evaluate time to radiographic progression after WBRT-HA/SIB for brain metastasis.
- 2.2.5 Evaluate overall survival after WBRT-HA/SIB for brain metastasis.
- 2.2.6 Evaluate adverse events according to CTCAE criteria.
- 2.2.7 Evaluate health-related quality of life [as assessed by the Functional Assessment of Cancer Therapy with Brain Subscale (FACT-BR) and the Euroqol EQ-5D before and after (WBRT-HA/SIB)]

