### 6.5 Critical Structures

- 6.5.1 Bilateral hippocampal contours will be manually generated on the fused 3D-SPGR MRI-planning CT image set by the treating physician according to contouring instructions.
- 6.5.2 Hippocampal avoidance regions will be generated by three-dimensionally expanding the hippocampal contours by 5 mm.
- 6.5.3 The lenses and orbits will be contoured as per the clinical experience of the treating physician. Care should be taken to minimize the dose to the lens and orbits.

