**Appendix II:**

**Follow-up Radiographic Assessment**

Date of MRI:

Patient Name:

Treated metastases

Lesion Number	Side (L,R,ML) & Location	d AP (cm) (Ant-Pos)	d ML (cm) (Med-Lat)	d SI (cm) (Sup-Inf)	Bidimensional product 
First set of treated metastases					
1					
2					
3					
4					
5					
6					
7					
8					
9					

 Bidimensional product = largest dimension x second-largest dimension

New Brain Metastases outside the hippocampus? (yes/no)

Number

New Brain Metastases within the hippocampus? (yes/no)

Number

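### The Appendix II form sorts new metastases by the hippocampus, while 11.6.1.1 sorts them by the hippocampal avoidance region, so the printed form would miss failures in the 5-mm rim

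*Combined protocol and SAP*

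**What the plan says.** Section 6.5.2 defines the region: "Hippocampal avoidance regions will be generated by three-dimensionally expanding the hippocampal contours by 5 mm". Section 11.6.1.1 uses it twice. The presence and number of "any new brain metastases within the hippocampal avoidance region (the hippocampus plus 5 mm) will be recorded on all follow-up forms", and "Recurrences will be categorized as either within the hippocampal avoidance region or elsewhere within the brain". The same section then lists three kinds of recurrence to be reported: in the brain, in the avoidance region, and elsewhere in the brain.

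The Appendix II follow-up form has two items on new lesions: "New Brain Metastases outside the hippocampus? (yes/no") and "New Brain Metastases within the hippocampus? (yes/no"), each followed by a number. The side-and-location column on that form belongs to the table of treated metastases. New lesions have no such column.

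The terms also vary elsewhere. Objective 2.2.3.3 reads "Evaluate local control within the hippocampal regions", without defining the regions. The sentence in 11.6.1.1 on new lesions in the rest of the brain subtracts an undefined hippocampal region, not the avoidance region.

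On lesion measurement, 11.6.1.1 records the bidimensional product of the 1-3 largest baseline metastases. The form has nine numbered rows for treated metastases. Sections 6.1.1.2 and 6.4.3 give every metastasis its own boost volume.

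**The concern.** Section 1.4 names the price of this technique: "Avoiding the hippocampus poses the risk of attenuating the benefit of WBRT due to increased metastatic disease within the hippocampal conformal avoidance region". It adds that no direct estimate of the risk of a new metastasis after hippocampal avoidance is currently possible, so this trial's own count has value. The tissue that is spared is the hippocampus plus its 5-mm rim, and a failure in the rim is a failure in spared tissue. A form that asks only about the hippocampus assigns that failure to the rest of the brain.

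What is at stake is the region label. It feeds objective 2.2.3.3 and the three-way recurrence report in 11.6.1.1. Events of this kind are expected to be few, so losing even one or two could turn a small count into a reported zero.

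**Working it through.** **1. The two rules side by side.** A new lesion lies in one of three places.

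| Site of new lesion | Category under 11.6.1.1 | Answer on the form as printed |
|---|---|---|
| Inside the hippocampal contour (*h* lesions) | Avoidance region | Within |
| In the rim, up to 5 mm from the contour (*r* lesions) | Avoidance region | Outside |
| More than 5 mm from the contour (*e* lesions) | Elsewhere | Outside |

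- Avoidance-region count: text *h* + *r*; form *h*.
- Elsewhere count: text *e*; form *e* + *r*.
- Total: *h* + *r* + *e* under both.

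The error is *r*. It always runs in the same direction, and it cancels in the total.

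**2. How large *r* can be relative to *h*.** The only relevant figures are in Section 1.4, from an imaging review of 100 patients at presentation.

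- Counts by distance: 9 + 11 + 17 + 235 = 272.
- Share within 5 mm: 9/272 = 3.31%, which reproduces the stated 3.3%.
- Inside the hippocampi: the protocol states that "none of the metastases lay within the hippocampi".

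So in that series *h* = 0, *r* = 9 and *e* = 272 − 9 = 263.

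- Avoidance-region count: text 0 + 9 = 9; form 0. Share captured: 0/9, with an exact two-sided 95% upper limit of 1 − 0.025^(1/9) = 0.336, or 34%.
- Elsewhere count: text 263; form 272. Overcount: 9/263 = 3.4%.

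The same nine lesions remove one category entirely and barely change the other.

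**3. What uses the label.**

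- Section 11.6.1.2 counts any new metastasis as CNS progression, wherever it lies, so time to radiographic progression does not change.
- Section 13.1.2 does not list local control as an endpoint, and 13.3 has no analysis of it, so no planned test changes.
- The primary endpoint and the sample size in 13.2 rest on HVLT-R delayed recall and do not use imaging.
- Objective 2.2.3.3 and the recurrence report in 11.6.1.1 do use it.

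**4. Secondary point: lesions measured.** With *k* boosted lesions, the text alone leaves *k* − 3 unmeasured when *k* > 3: 4 − 3 = 1 of 4, and 9 − 3 = 6 of 9. Section 3.2.1 allows up to 9 lesions. The form, with nine rows, leaves none unmeasured. Text and form therefore differ only in patients with four or more lesions.

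**The case against.** The strongest reply is that the form should be read with its instructions. Section 11.6.1.1 says what goes on the follow-up forms, and the two form items match its two sentences one for one. On that view, hippocampus on the form is shorthand for the avoidance region, and a careful reader would class a rim lesion correctly. This is possible, so the undercount depends on the form being completed as printed. But nothing on the form mentions the margin or refers back to 11.6.1.1, and nothing else recorded there would reveal the error.

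The second reply is that little follows from it. Much of that stands: no planned test changes, and Section 12.0 collects progression scans and reports, so the label can be recovered. However, the plan provides for no such re-reading, and the protocol does promise a report by region.

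The third reply is that the 9 of 272 are lesions at presentation in another series. That also stands. They show how the wording behaves, not how often it will matter here.

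**Conclusion.** The mismatch between text and form is plain on the page. If the form is followed literally, avoidance-region failures are undercounted and failures elsewhere overcounted by the same number. In the cited series, none of the nine lesions concerned would be captured. Carrying that pattern over to new lesions assumes that they are distributed as at presentation, which is the assumption 1.4 itself makes. The number affected in this trial is probably small, because few lesions in that series lay near the hippocampi and the target is 50 patients. The correction is worth making, but it touches only the regional result.

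Four stronger readings go beyond the documents:

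- **A patient count.** A reader might multiply 50 registered × 40% alive at 3 months × 50% intracranial failure × 8.6% with a lesion within 5 mm: 50 × 0.40 × 0.50 × 0.086 = 0.86. This chains a 3-month survival assumption, a 6-month control figure from WBRT without hippocampal avoidance, and an incidence at presentation. The result is not an estimate for this trial.
- **A biased progression endpoint.** Any new lesion counts as progression whatever its label.
- **Only three lesions are ever measured.** That is true of the text in 11.6.1.1, but the form has room for nine. The supported finding is that the two differ.
- **Rim lesions are formally excluded at entry.** Section 1.4 says such patients are not eligible, but 3.2 lists no such exclusion, and 3.1.2 asks only for measurable disease outside the margin. The point does not need this premise, because the form items concern new lesions.

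**What to change.** - Reword both Appendix II items to ask about new metastases within and outside the hippocampal avoidance region (hippocampus plus 5 mm).
- Use the same term in objective 2.2.3.3 and in the 11.6.1.1 sentence on the rest of the brain.
- Add a location entry for each new lesion.
- Re-class new lesions already recorded, using the existing scans and the planning contours from 6.5.2.
- For the secondary point, state that all boosted lesions on the nine-row form are used for objective 2.2.3.1, and that tracked lesions in 11.6.1.2 are the 1-3 largest, so that the progression rule is unchanged.

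The cost is two reworded form items, one added entry and a few words of text. Re-reading is needed only for patients with a new lesion already on record: at most the 32 in the internal pilot plus any enrolled since. Measuring all boosted lesions adds up to 9 − 3 = 6 measurements per scan in a patient with nine lesions, compared with the text as it stands, and the form already has the rows for them.

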11.6.1.2 Definition of CNS Progression

CNS progression will be defined as a defined increase (see below) in perpendicular bidimensional tumor area for any of the tracked brain metastases, or the appearance of any new brain metastasis on a follow-up MRI.

For lesions < 1cm in maximum diameter, a minimum increase of 50% of perpendicular bi-dimensional treatment area will be necessary to score as progression. This caveat is included to account for potential variability in measurement, which will be most susceptible to proportionate errors at smaller sizes.

For lesions > 1cm in maximum diameter, the definition will use a 25% rule for change.

11.7 Criteria for Discontinuation of Protocol Treatment

11.7.1 Unacceptable adverse event to the patient (at the discretion of the treating physician)—Reasons for removal must be clearly documented on the appropriate case report form/flowsheet.

11.7.2 Interruption of treatment of >3 days

If protocol treatment is discontinued, follow-up and data collection will continue as specified in the protocol but the patient will be considered inevaluable.

## **12.0 DATA COLLECTION**

### Summary of Data Submission

Item	Due
Demographic Form	Within 2 weeks of registration
Initial Evaluation Form	
Mini-Mental Status Exam	
Neurocognitive Evaluation Summary Form (HVLTR, TMT, COWAT)	Before the first treatment
Fatigue Evaluation Summary, FACT-BR, EQ-5D	
Follow-up Forms	3, 6, 9, 12, and 24 months after radiotherapy is completed
Mini-Mental Status Exam	
Neurocognitive Evaluation Summary Form (HVLTR, TMT, COWAT)	
Fatigue Evaluation Summary	
Quality of life Assessments (FACT-BR, EQ-5D)	As above
Progression MRI Scan & Report	Within 1 week of scan date

## **13.0 STATISTICAL CONSIDERATIONS**

### 13.1 Study Endpoints

#### 13.1.1 Primary Endpoint

Delayed recall, 3 months from the start of treatment as measured by the Hopkins Verbal Learning Test-Revised for delayed recall (HVLTR delayed recall)

#### 13.1.2 Secondary Endpoint

- 13.1.2.1 Cognitive function includes the HVLTR for free recall, and delayed recognition; the Controlled Word Association Test (COWAT); the Trail Making Test Parts A and B (TMT); the Medical Outcomes Scale-Cognitive Functioning Subscale (MOS); the Mini-Mental Status Examination (MMSE) after WBRT-HA/SIB for brain metastasis
- 13.1.2.2 Fatigue as measured by the Multidimensional Fatigue Inventory (MFI-20)
- 13.1.2.3 Time to radiographic progression
- 13.1.2.3 Overall survival
- 13.1.2.5 Adverse events based on CTCAE criteria

### 13.2 Sample Size

The primary endpoint will be delayed recall, as measured by the relative (percent) change in HVLTR delayed recall score from the start of treatment to 3 months after the start of treatment.

The sample size calculation will address the specific primary hypothesis that WBRT-HA/SIB reduces decline in delayed recall (from baseline to 3 months). We do not expect improvement in delayed recall; at best, we anticipate a preservation of delayed recall. Data from a randomized trial showed that the decline in HVLTR delayed recall score was 64% at 4 months for those getting whole brain radiation for brain metastases (Chang et al., 2009). We anticipate that WBRT-HA/SIB will have better delayed recall functioning at 3 months than WBRT alone. Detecting a 30% average relative loss due to WBRT-HA/SIB suggests a 50% relative improvement over previous results. The null and alternative hypotheses are:

$$H_0: \Delta HVLTR = 0.60 \text{ vs. } H_A: \Delta HVLTR \leq 0.30$$

$\Delta$ HVLT-R is the mean of relative decline between baseline and 3 month after treatment in this patient population. For patient individual i, the relative decline is calculated as follows:  $\Delta$ HVLT-Ri = ( HVLT-Ri0 - HVLT-Ri3 ) / HVLT-Ri0 , where HVLT-Ri0 and HVLT-Ri3 denote individual patient scores at baseline and 3 months after treatment, respectively.

Initial sample size calculation:

Based on the one-sided one sample t-test, assuming a standard deviation of 41%, with alpha=0.05 (one-sided), a total of 9 analyzable patients would ensure 80% statistical power to detect a 30% average relative loss in delayed recall at 3 months. Assuming a death rate of 60% prior to 3 months and a 10% in-evaluable rate, the target sample size will be 34 registered patients.

Sample size re-estimation based on internal pilot study:

The internal pilot consists of 32 patients enrolled at baseline, among which 9 patients have complete information on HVLT-R delayed recall score at the start of treatment and 3 months after the start of treatment. For the 9 patients, the mean and standard error of relative (percent) change (decline) in HVLT-R delayed recall score is 31% and 51%. We re-estimate the required sample size using the updated standard error.

Based on the one-sided one sample t-test, assuming a standard deviation of 51%, with alpha=0.05 (one-sided), a total of 18 analyzable patients would ensure 80% statistical power to detect a 30% average relative loss in delayed recall at 3 months. Assuming a death rate of 60% prior to 3 months and a 10% in-evaluable rate, the target sample size will be 50 registered patients. Therefore, additional 18 patients need to be recruited at the second stage.

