In an attempt to disentangle these confounding effects, a detailed analysis was published of the time course of NCF decline in eight prospectively measured domains in 208 brain metastases patients treated with 30 Gy of WBRT (Li 2007). NCF, assessed by tests of memory, executive function, and fine motor coordination, was correlated with metastasis volume regression as measured by magnetic resonance imaging. NCF and survival were compared in 135 patients evaluable at 2 months with tumor shrinkage less than (poor responders) and greater than (good responders) the population median. The mean NCF scores and brain metastasis volume at 4 and 15 months were compared. Good responders experienced significantly improved survival (unidirectional  $p = 0.03$ ). For all tests, the median time to NCF deterioration was longer in the good than in the poor responders, with statistical significance seen for executive and fine motor functions. In long-term survivors, defined as patients surviving more than 15 months, tumor shrinkage was significantly correlated with preservation of executive function and fine motor coordination ( $r = 0.68-0.88$ ). These findings support two important possibilities. First, achieving local control with WBRT was integral to both improving survival and preserving certain NCF domains. Second, an intriguing exception to these findings was memory function, specifically recall and delayed recall as assessed with the Hopkins Verbal Learning Test (HVLTR). These NCF domains appeared to have a weaker association with tumor reduction and were the most susceptible to early decline, even in patients with non-progressing brain metastases, implying the selective effect of WBRT in preserving certain domains over others and the differential sensitivity of certain domains to radiation effects.

Further evidence of the early susceptibility of memory function to WBRT was recently demonstrated by Chang and colleagues (2009). They reported a single-institution phase III trial of stereotactic radiosurgery (SRS) with or without WBRT in patients with one to

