## 1.7 Summary and Historical Control

In summary, preclinical and clinical evidence suggests that radiation dose received by the hippocampus during WBRT may play a role in radiation-induced neurocognitive decline. Although neurocognitive assessment in patients receiving WBRT can be confounded by intracranial metastatic disease, analyses suggest a differential sensitivity of various neurocognitive domains, such as delayed recall, to WBRT. This provides the rationale to explore the clinical feasibility of hippocampal avoidance during WBRT. The dosimetric capabilities of IMRT to conformally avoid the hippocampus without detriment to the

radiation dose the remaining brain receives has been demonstrated, as well. Through retrospective analyses, we have also estimated the theoretical risk of perihippocampal disease progression with hippocampal avoidance. Given the overall aim of prolonging neurocognitive decline, and the possibility of salvaging hippocampal and perihippocampal recurrences with radiosurgery, we hypothesize that WBRT with HA and SIB (WBRT-HA/SIB) will provide a net gain in this endpoint.

In this phase II study, we plan to treat patients with brain metastases with WBRT-HA/SIB. To assess the utility of WBRT-HA/SIB, a comparison of these endpoints with historical data of WBRT without hippocampal avoidance will be necessary to determine whether a phase III prospective randomized trial of WBRT with and without hippocampal avoidance would be warranted, and if so, what statistical considerations would be needed. We plan to utilize data from the control arm (WBRT alone) of a recent phase III trial (PCI-P120-9801) of motexafin gadolinium and WBRT (30 Gy/10 fractions) versus WBRT alone in 401 patients with brain metastasis (PI: Mehta) (Mehta 2003; Mehta 2002). These phase III data serve as a particularly useful control for our phase II study, given the similarities in inclusion criteria and study design.

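### Rejecting the 0.60 null would not show benefit over WBRT alone, because Section 13 never specifies the comparison that Section 1.7 calls necessary; and the primary endpoint is dated from treatment start although the only scheduled visit is counted from the end of radiotherapy

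*Combined protocol and SAP*

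**What the plan says.** **Comparator.** Section 1.7 states that "a comparison of these endpoints with historical data of WBRT without hippocampal avoidance will be necessary". The purpose it gives is the decision on the next trial, namely "to determine whether a phase III prospective randomized trial of WBRT with and without hippocampal avoidance would be warranted". It names the source: "We plan to utilize data from the control arm (WBRT alone) of a recent phase III trial (PCI-P120-9801) of motexafin gadolinium". It adds: "These phase III data serve as a particularly useful control for our phase II study".

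Section 13.2 uses a different source. It reports that the decline in HVLT-R "delayed recall score was 64% at 4 months for those getting whole brain radiation for brain metastases", from a cited randomized trial, and then sets H0 at a mean relative loss of 0.60 against 0.30 or less. It says "We anticipate that WBRT-HA/SIB will have better delayed recall functioning at 3 months than WBRT alone" and that a 30% loss "suggests a 50% relative improvement over previous results". Section 1.1 describes the cited trial as a "single-institution phase III trial of stereotactic radiosurgery (SRS) with or without WBRT in patients with one to" (the upper limit is three metastases), and reports its arms as SRS+WBRT and SRS alone.

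Section 13.3.1 specifies a one-sided one-sample t-test at 0.05 against this null. Nothing in 13.2 or 13.3 refers to PCI-P120-9801 or to a comparison with historical patients.

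**Time point.** Sections 13.1.1, 13.2 (opening sentence and pilot paragraph) and 13.3.1 place the primary endpoint 3 months from the start of treatment. Objective 2.1, the formula text in 13.2, Section 11.5.1.1, Section 12.0 and Appendix I count from after radiotherapy. Section 6.1.1.1 gives radiotherapy a length of 2 to 2.5 weeks.

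**The concern.** In a single-arm trial the null value is the comparator, so its source decides what a rejection means. Section 1.7 ties the phase III decision to a comparison with WBRT alone, and 13.2 voices an expectation about WBRT alone, yet the planned test compares with a fixed 0.60 whose cited source is an SRS+WBRT arm. A positive result reported beside that expectation could be taken as benefit over WBRT alone, which the test does not address. The comparison that would address it has no analysis in Section 13.

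The second issue is narrower. The primary endpoint is defined, in the sections that govern the analysis, at a date for which no neurocognitive visit is scheduled. No visit window is given, and 13.2 uses both time origins.

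**Working it through.** **Inputs.** From 13.2: null 0.60, alternative 0.30, SD 0.51, one-sided alpha 0.05, 18 analyzable, 60% deaths before 3 months, 10% inevaluable, 50 registered, 9 complete cases among 32 pilot patients. From 6.1.1.1: 14 to 17.5 days of radiotherapy.

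**1. The plan's own figure.** Normal approximation: n = ((1.645 + 0.842) × 0.51 / 0.30)² = 17.87, so 18. Registered: 18 / (0.40 × 0.90) = 50. Both reproduce. (By the t-test that the plan names, power at 18 is 77.3%; that is a separate matter.)

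**2. What a rejection shows.**
- SE = 0.51 / √18 = 0.1202; t(0.95, 17 df) = 1.740; 1.740 × 0.1202 = 0.209.
- H0 is rejected when the observed mean loss is below 0.60 − 0.209 = 0.391.
- An on-target mean of 0.30 has a one-sided 95% upper bound of 0.30 + 0.209 = 0.509.

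The second line supports a mean loss below 0.60, and the third a mean loss below about 0.51. Neither says anything about WBRT alone unless a WBRT-alone mean is known.

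**3. Position of 0.60 against the cited 64%.** At n = 18 and SD 0.51 (noncentral t), a regimen with a true mean loss of 0.64 rejects H0 with probability 2.5%, below the nominal 5%. The step from 64% to 0.60 is therefore conservative. The stated 50% improvement is 1 − 0.30/0.60; against 64% it is 1 − 0.30/0.64 = 53%.

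**4. Sensitivity to an unknown WBRT-alone mean (assumed values; none is in the documents).**

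| True mean loss with no benefit | Probability of rejecting 0.60 |
|---|---|
| 0.64 | 2.5% |
| 0.60 | 5.0% |
| 0.55 | 10.7% |
| 0.50 | 19.9% |

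If the 1.7 comparison were done with 30 to 150 assessed control patients and SD 0.51 (both assumed), the SE of the difference would be 0.152 to 0.127. An on-target 0.30 would then exclude zero difference, by a one-sided 95% bound, only if the WBRT-alone mean were above about 0.56 (30 controls) to 0.52 (150 controls).

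**5. Time origin in days.** Three months is 91.3 days. The scheduled visit falls at 91.3 + 14 = 105.3 to 91.3 + 17.5 = 108.8 days from treatment start.

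**6. Effect of the origin on numbers.** The pilot has already given 9 complete cases, so only the further 18 registrations are affected.
- If the 60% death rate runs to the scheduled visit: 9 + 18 × 0.40 × 0.90 = 15.5.
- If it runs only to 3 months from start (constant hazard assumed), survival to the visit is 0.4^(105.3/91.3) = 0.348 to 0.4^(108.8/91.3) = 0.336. The count is 9 + 18 × 0.348 × 0.90 = 14.6 to 9 + 18 × 0.336 × 0.90 = 14.4.

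The difference is about one patient. This assumes that no other pilot patient was still awaiting the visit; the documents do not say.

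**The case against.** Section 1.7 offers its comparison as a guide to phase III and does not say that PCI-P120-9801 must set the phase II null, so drawing H0 from another source is not a contradiction. The regimen includes a boost, and Section 1.3 says that boost doses similar to radiosurgery can generally be reached; an SRS+WBRT arm may thus be a closer match than WBRT alone. The 0.60 is stricter than the cited 64%. The words about WBRT alone are an expectation, and no section says that a rejection will be reported as benefit over WBRT alone. The time-point gap is about two weeks, and only one assessment near 3 months exists, so no rival data point competes with it.

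Most of this stands. The choice of benchmark is a design preference, and the missing step from 64% to 0.60 is only missing detail. What remains is that 1.7 calls a comparison necessary and Section 13 does not provide one, while 13.2 names a comparator that its source did not study. The origin is mixed in the definition of the primary endpoint itself, however small the gap.

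Stronger readings that a reader might infer are not supported:
- **That the 64% is a share of patients declining.** Section 13.2 calls it a decline in score. The probability of a drop of more than 5 points in Section 1.1 is another measure, at 3 months rather than 4.
- **That 0.60 is too lenient against WBRT alone.** No document gives a WBRT-alone loss, so the error could lie in either direction.
- **That the time origin explains a fall from 18 to 15 or 16 analyzable patients.** The fall to 15.5 comes from the pilot's yield of 9 of 32; the origin accounts for about one patient more.

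**Conclusion.** The point holds in limited form, at a severity between minor and should-fix. The planned test can support a mean relative loss below 0.60 among assessed patients. It cannot support benefit over WBRT alone, and the comparison that Section 1.7 requires for that purpose is absent from 13.2 and 13.3. The rejection threshold (0.39) and the on-target upper bound (0.51) rest only on the plan's SD of 0.51 and 18 analyzable patients. The rejection rates at 0.55 and 0.50 and the control-arm thresholds rest on assumed values and are illustrations.

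The primary time point is inconsistent by 14 to 17.5 days, and only the post-radiotherapy visit is scheduled. Its effect on expected numbers is about one patient under a constant hazard; its importance is that the primary endpoint should have one definition.

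**What to change.** 1. **Keep H0 at 0.60.** It should not move now that the pilot mean of 31% has been seen. Add to 13.3.1: *Rejection of H0 will be reported as a mean loss below the 0.60 benchmark among assessed patients, and not as benefit over WBRT alone unless the comparison in 1.7 is done.*
2. **Reconcile 1.7 with 13.3.** If the PCI-P120-9801 data are available, add the comparison to 13.3 as a supportive estimate: the same relative-decline formula, the closest visit, and a difference that carries both standard errors. If they are not, amend 1.7.
3. **Use one time point.** Check the dates of the nine pilot assessments. Then define the primary time point in 13.1.1, 13.2 and 13.3.1 as the scheduled visit 3 months after completion of radiotherapy, and report each analysed patient's assessment day. State in 13.2 to which date the 60% death rate runs.

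Cost: wording in three sections, a check of nine dates, and either one supportive analysis or an amendment to 1.7. The supportive analysis needs individual scores from another trial; the documents show neither access to them nor a matching visit, so it may not be possible. Null, alpha and sample size do not change. The downside is a possibly less favourable claim.
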